11.2.2. Severity of Events

The following definitions should be considered when evaluating the severity of AEs and SAEs:

Severity of	Event
Mild	Symptom(s) barely noticeable to subject or does not make subject uncomfortable; does not influence performance or functioning; prescription drug not ordinarily needed for relief of symptom(s) but may be given because of personality of subject.
Moderate	Symptom(s) of a sufficient severity to make subject uncomfortable; performance of daily activity is influenced; subject is able to continue in study; treatment for symptom(s) may be needed.
Severe	Symptom(s) cause severe discomfort; symptoms cause incapacitation or significant impact on subject's daily life; severity may cause cessation of treatment with study treatment; treatment for symptom(s) may be given and/or subject hospitalized.

11.3. Monitoring and Recording Events

11.3.1. Adverse Events

Adverse events will be collected during the period between informed consent and 7 days after the second follow-up visit (about 90+7 days after the index stroke).

11.3.2. Serious Adverse Events

Any SAE experienced by a subject after the subject signs the informed consent form (ICF) and before the final follow-up visit is to be recorded on an SAE Form. For reporting timelines and procedures, see Section 11.3.3.

Subjects will be followed for all SAEs until 7 days after the second MRI and PET scan (i.e. 90days after the index stroke)

Any SAE ongoing when the subject completes the study or discontinues from the study will be followed by the Investigator until the event has resolved, stabilized, or returned to baseline status.

11.3.3. Immediate Reporting of Serious Adverse Events

The Investigator will notify the local ethics committee per local requirements and report applicable events to Heath Authorities as required by local legislation.

The study site must formally notify Biogen SABR within 24hours of the study site staff becoming aware of the SAE. It is the Sponsor-Investigator's responsibility to ensure that the SAE reporting information and procedures are used and followed appropriately. Site Principal Investigators must report SAE to the Sponsor-Investigator within 24 hours of becoming aware of the event.

11.3.4. **Deaths**

Death is an outcome of an event. The event that resulted in death should be recorded and reported on the appropriate CRF. All causes of death must be reported as SAEs. The Investigator should make every effort to obtain and send death certificates and autopsy reports to Biogen SABR.

11.4. Procedures for Handling Special Situations

11.4.1. Reporting Pregnancy

The Investigator should refer to the approved local label for guidance if female subjects become pregnant.

11.4.2. Medical Emergency

In a medical emergency requiring immediate attention, study site staff will apply appropriate medical intervention, according to current standards of care.

11.5. Chief Investigator Responsibilities

The Sponsor- Investigator's responsibilities include the following (refer to Section 11.3.1for details):

- Review all AEs to determine seriousness and fulfillment of collection criteria
- Monitor and record all SAEs
- Determine the onset and resolution dates of each SAE
- Record all pregnancies.
- Complete the appropriate form for each SAE and fax or email it to Biogen SABR within 24 hours of the study site staff becoming aware of the event.

- Pursue SAE follow-up information actively and persistently. Follow-up information
 must be reported to Biogen SABR within 24 hours of the study site staff becoming
 aware of new information.
- Ensure all SAE reports are supported by documentation in the subjects' medical records.
- Report SAEs Biogen, local ethics committees, Health Authorities, other Investigators and entities as required by local law.

12. STATISTICAL CONSIDERATIONS

12.1. Sample Size Justification

This is a natural disease progression study. Quantitative data on the uptake in and around infarcts and changes over time are not available to base a power calculation on. Therefore, sample size has been determined pragmatically, based on feasibility. The main purpose is to pilot characterization of the magnitude and variability of the change in a normalized measure of the TSPO radioligand uptake in the target regions between baseline (14 days) and 90 days post infarction in untreated patients. We chose to use a pseudo-reference region quantification as it avoids the need for radial artery cannulation in these patients. In addition, this method has a significantly better test-retest variability than the fully quantitative methods using metabolite corrected arterial plasma input function (\sim 4-5% vs \sim 20%)...²² . While such an approach may lead to an underestimation of any changes seen, ²³ due to potential changes in signal in the pseudo-reference region, we believe it is justified in this situation where a focal change in signal is expected, and will be compensated for by reduced signal variability.

The magnitude of the signal change between days 14 and 90 is unknown but it is expected that changes above 10% will be detectable given the small test/retest variability of [11C]PBR28.

12.2. Analysis Population

All eligible subjects who have completed at least one PET-MRI scan will be included in the analysis

12.3. Methods of Analysis

In general, summary statistics will be presented. Continuous variables will be summarized using descriptive statistics, and categorical variables will be presented using frequency distributions.

12.4. Endpoints Analysis

PET-derived measures including SUVR in the infarct and peri-infarct area, and ROIs distant from the infarct area at Day 15 and Day 90 will be summarized by visit. Various aspects of change over time including magnitude, variability and pattern will be assessed. The relationship between PET-derived measures and stroke severity (including stroke volume, size, NIHSS) will be examined using methods including linear correlation and regression. Also, the relationship between PET-derived measures and functional outcomes , markers of systemic inflammation and relationship between measures of white matter tract injury and measures of thalamic uptake will be explored.

A detailed statistical analysis plan will be established before the beginning of the analysis.

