- To characterize post-stroke TSPO glial expression in relation to measures of stroke severity (infarct size, volume and location; NIHSS) and functional outcome (mRS,BI, depression scale, MoCA)
- To characterize post-stroke TSPO glial expression in relation to systemic inflammatory markers in blood

The endpoints that relate to these objectives are:

- PET-derived measures of TSPO radiotracer uptake in the infarct and peri-infarct areas at day 15 and day 90 after a stroke
- PET-derived measures of TSPO radiotracer uptake in ROIs distant from the infarct area (e.g. thalamus, hippocampi, amygdalae and midbrain) at day 15 and day 90 after a stroke
- Correlation of PET-derived measures with clinical and imaging measures of stroke severity (stroke volume, size and NIHSS) and functional outcome (mRS Barthel index, MoCA, depression,) at day 15 and day 90
- Correlation of infarct volume and MRI measures of white matter tract injury determined from DTI MRI with measures of thalamic TSPO uptake (timeactivity curve; measures of mean and max TSPO uptake on summed image sets from TSPO PET
- Correlation of PET derived measures with inflammatory markers in the blood (e.g. cytokines)

Study Design: This is an exploratory, prospective, natural history, imaging

cohort study.

Study Location and Number

of Sites:

The recruiting site will be Imperial College Healthcare NHS

Trust. All study scans will be performed by Imanova,

Hammersmith Hospital

Number of Planned Subjects: Between 15 and 25 subjects, with recruitment ending when

15 participants have completed all study procedures.

Study Population: Subjects aged 18-85 with a supratentorial ischemic stroke of

moderate severity as measured by NIHSS >4 and evidence

of infarction on clinical brain scan at time of stroke:

Duration of Treatment and

Follow-up:

Subjects will participate in this study for approximately 90

days. No treatment will be started as part of the trial

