4. SCHEDULE OF EVENTS

Tests and Assessments	Screening visit ⁹	Day 15 (±3 days)	Day 90 (±7 days)
Eligibility confirmation ¹	X		
Sign Informed Consent Form ²	X		
Demographics and medical history	X		
Physical and neurological examination	X	X	X
Vital signs ³	X	X	X
Height (if available) and weight	X		
Urine (or serum) pregnancy test ⁴	X	X	X
Medications	X		
NIHSS		X	X
mRS		X	X
BI		X	X
Beck Depression Inventory		X	X
Hematology and blood chemistry ^{5,6}	X		
Blood sample for systemic inflammatory profile	X	X	X
Blood sample for TSPO polymorphism genotyping ⁷	X		
Confirmation of genotype eligibility criterion ⁸		X	
PET and MRI scanning		X	X
Adverse Events reporting		throughout	

- 1. All but genotype exclusion criterion, see bullet point 8
- 2. Subjects will be consented prior to screening procedures
- 3. Vital signs include temperature, blood pressure, pulse or heart rate and respiratory rate
- 4. Women with childbearing potential only
- 5. Liver function, renal function and CBC will be performed at screening. Results of tests performed as part of standard of care can be accepted.
- 6. Renal function tests will be repeated before each PET MRI assessment in subjects older than 60 years of age or with known renal impairment
- 7. SNP genotype confirmation is required to determine eligibility. Blood samples for this assessment will be collected at screening only after other eligibility criteria have been met
- 8. Verification of the TSPO SNP genotype exclusion criterion will occur prior to or at the PET MRI acquisition day but will be confirmed before subjects undergo PET-MRI imaging acquisition.

CONFIDENTIAL

The information contained herein may not be used, disclosed, or published without the written consent of the Sponsor-Investigator.

9. Up to 10 days from stroke onset

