6. STUDY OBJECTIVES AND ENDPOINTS

6.1. Objectives and Endpoints

The objectives of this study are:

- To characterize TSPO glial expression in specific regions of interest defined on correlative brain MRI (ROIs; infarct, peri-infarct, thalamus) in the subacute (day 15+3) and chronic (day 90+7) phases after an ischemic stroke;
- To determine the magnitude and variability of TSPO uptake at these ROIs during the assessment period;
- To describe changes in TSPO expression between 15 and 90 days
- To explore the relationship between TSPO uptake, blood and infarct volume, and measures of Wallerian degeneration; and,
- To characterize post-stroke TSPO glial expression in relation to measures of stroke severity (infarct size, volume and location; NIHSS) and functional outcome (mRS, BI, MoCA, Beck depression inventory)
- To characterize post-stroke TSPO glial expression in relation to systemic inflammation in blood

Endpoints that correlate to these objectives are:

- PET-derived measures of TSPO radiotracer uptake in the infarct and peri-infarct areas at day 15 and day 90 after a stroke;
- PET-derived measures of TSPO radiotracer uptake in ROIs distinct from the infarct area (e.g., thalamus, hippocampi, amygdalae and midbrain) at day 15 and day 90 after a stroke:
- Correlation of PET-derived measures with clinical and imaging measures of stroke severity (stroke volume, size and NIHSS) and functional outcome (mRS and BI) at day 15 and day 90
- Correlation of infarct volume and MRI measures of white matter tract injury determined from DTI MRI with measures of thalamic TSPO uptake (time-activity curve; measures of mean and max TSPO uptake on summed image sets from TSPO PET.
- Correlation of PET derived measures with inflammatory markers in the blood (e.g. cytokines)

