8. STUDY POPULATION

8.1. Inclusion Criteria

To be eligible to participate in this study, candidates must meet the following inclusion criteria at screening:

- 1. Able to understand the purpose and risks of the study and provide signed and dated informed consent and authorization to use protected health information in accordance with national and local subject privacy regulations in accordance with all local and national regulations OR according to the local institutional review board's (IRB's)/ethics committee's (EC's) guidelines OR by another process compliant with applicable national laws and regulations and IRB/EC requirement
- 2. Aged 18-85 years of age at the time of informed consent
- 3. Clinical diagnosis of supratentorial acute ischemic stroke within the previous 10 days. Note: An acute brain CT or MRI scan must be available from the patient's history to assess eligibility for the study and be consistent with the diagnosis of acute ischemic stroke.
- 4. Score of at least 5 points on the NIHSS at Screening.
- 5. Subjects of childbearing potential (male and female) must be willing and able to practice effective contraception during the study and for 4 weeks after their Day 90 appointment.
- 6. Negative serum/ urine pregnancy test on all females of childbearing potential within 2 days before each PET study.

8.2. Exclusion Criteria:

Candidates will be excluded if any of the following exclusion criteria exist at screening, or at the time point specified in the individual criterion listed:

- 1. Unable or unwilling to provide informed consent.
- 2. Presence of acute intracranial hemorrhage on acute brain CT or MRI
- 3. Inability to comply with study requirements (including implanted pacemaker).
- 4. Subject has contraindications to undergoing MRI examination (including, but not limited to metal foreign bodies incompatible with MRI exposure, cardiac pacemakers, renal impairment that contraindicates gadolinium etc.) or PET scan.
- 5. Subject has participated in a research and/or medical protocol involving nuclear medicine, PET or radiological investigations with radiation exposure that, when combined with the radiation exposure from the present study, would exceed 10 mSV in addition to the natural background radiation, in the previous 12 months.
- 6. Other unspecified reasons that, in the opinion of the Investigator make the subject unsuitable for enrollment.

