10.2. Clinical Assessments

After providing informed consent, the medical history will be documented in a CRF. Patients will also undergo a neurological examination. On the day of the PET and MRI examinations, the patients will be asked for the any events in the interim period since the screening examination. They will undergo a physical examination with a focus on neurological findings. Specifically, they will be assessed using the following tools: **mRS:** The mRS measures independence, rather than neurological function, with specific tasks pre- and post stroke ¹⁴⁻¹⁷. The scale consists of 7 grades, from 0 to 6, with 0 corresponding to no symptoms and 6 corresponding to death. The premorbid mRS will be scored through interviews with the participant and/or family caregiver. Raters will be required to be certified in the use of the mRS. The mRS will be completed by a telephone interview for any subjects who fail to attend their Day 90 Follow-Up or Early Termination visit. The mRS takes less than 5 minutes to administer.

BI: The BI consists of 10 items that measure a person's daily functioning, specifically the activities of daily living and mobility ¹⁸⁻²⁰. The items include feeding, moving from wheelchair to bed and returning, grooming, transferring to and from a toilet, bathing, walking on a level surface, going up and down stairs, dressing, and maintaining continence of bowels and bladder. The assessment can be used to determine a baseline level of functioning and can be used to monitor change in activities of daily living over time. The items are weighted according to a scheme developed by the authors. The person receives a score based on whether they have received help while doing the task. The scores for each of the items are summed to create a total score up to a maximum of 100. The higher the score, the more "independent" the person is. The BI takes less than 5 minutes to administer.

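### The Screening NIHSS needed for entry is missing from the Schedule and from every endpoint and analysis, so clinical stroke severity rests on NIHSS taken at the outcome visits

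*Combined protocol and SAP*

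**What the plan says.** The objectives in 6.1 treat stroke severity (infarct size, volume and location, and NIHSS) and functional outcome (mRS, BI, MoCA, Beck inventory) as two separate things to relate to TSPO uptake. The matching endpoint is "Correlation of PET-derived measures with clinical and imaging measures of stroke severity (stroke volume, size and NIHSS"; the same bullet goes on to "functional outcome (mRS and BI) at day 15 and day 90". Section 12.4 says "The relationship between PET-derived measures and stroke severity (including stroke volume, size, NIHSS) will be examined using methods including linear correlation and regression", gives no time point for NIHSS, and defers detail to a later SAP.

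The entry score appears in two places. Criterion 4 in 8.1 reads "Score of at least 5 points on the NIHSS at Screening". The synopsis describes the study population as of "moderate severity as measured by NIHSS >4 and evidence" of infarction on the clinical scan. A footnote to the Schedule of Events sets the Screening visit at "Up to 10 days from stroke onset".

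The NIHSS row of the Schedule is marked at Day 15 and Day 90 only; its Screening cell is empty. The Clinical Assessments section (the second section numbered 10.2) introduces the scales under the scan visits: "On the day of the PET and MRI examinations, the patients will be asked for the any events in the interim period since the screening". A clinical check-up and the named tools then follow, NIHSS among them.

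**The concern.** The protocol uses the entry NIHSS to say how severe the strokes are, then gives that score no analytic role. The only scheduled NIHSS values come from the visits at which mRS and BI are also taken. At Day 90 a severe stroke that recovered and a milder one that did not can score alike, so that NIHSS reflects initial severity and recovery together. The same is true of Day 15 to a smaller degree.

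What is at stake is how the clinical severity correlation can be read. Table 1 of the protocol cites an earlier study in which persistent uptake went with worse clinical outcome. If this cohort shows a similar association, a natural next question is whether uptake follows the size of the initial insult or the course afterwards. Without the entry score in the analysis, no clinical measure of the initial insult is available to help answer it. A weak correlation with a later NIHSS would also be hard to interpret.

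**Working it through.** The plan states no alpha, power or effect size for this analysis, and 12.1 says that the sample size was set on feasibility. There is therefore no figure of the plan's own to reproduce. The main check is a comparison of sections; the arithmetic after it is illustrative.

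**1. Where NIHSS appears**

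| Place | NIHSS at Screening | NIHSS at Day 15 / Day 90 |
|---|---|---|
| 8.1, criterion 4 | required, at least 5 | – |
| Synopsis, study population | describes severity, above 4 | – |
| Schedule of Events | cell empty | marked at both |
| Clinical Assessments | not named | on scan days |
| 6.1, endpoint bullet | not named | bullet closes with both days |
| 12.4 | not named | no time point given |

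The score is required for entry, but it is not scheduled and not used.

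**2. Gap between the entry score and the later scores**

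Inputs from the Schedule: Screening on days 0–10, first scan visit on days 15 ± 3 = 12–18, second on days 90 ± 7 = 83–97.

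- Entry to Day 15: shortest 12 − 10 = 2 days; longest 18 − 0 = 18 days.
- Entry to Day 90: shortest 83 − 10 = 73 days; longest 97 − 0 = 97 days.

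The two scores may be nearly the same measurement for a late-screened patient at Day 15. They are well separated for every patient at Day 90.

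**3. Illustration of lost signal (assumed correlations)**

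Assume that uptake correlates 0.60 with entry NIHSS, that a later NIHSS relates to uptake only through entry severity, and that entry and later NIHSS correlate at r₁₂. The expected correlation of uptake with the later score is then 0.60 × r₁₂. Approximate power is Φ(atanh(r)·√(n−3) − 1.96), for a two-sided 0.05 level that is assumed here. The synopsis plans 15 to 25 subjects, with 15 completers.

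| r₁₂ | Expected r | Power, n = 15 | Power, n = 25 |
|---|---|---|---|
| 0.5 | 0.30 | 19% | 31% |
| 0.7 | 0.42 | 34% | 56% |
| 0.8 | 0.48 | 44% | 69% |
| 0.9 | 0.54 | 55% | 81% |
| entry score itself | 0.60 | 67% | 90% |

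Worked line, r₁₂ = 0.8 and n = 15: 0.60 × 0.8 = 0.48; atanh(0.48) = 0.523; 0.523 × √12 = 1.81; 1.81 − 1.96 = −0.15; Φ(−0.15) = 44%.

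The smallest |r| reaching two-sided p < 0.05 is t/√(n−2+t²). At n = 15 (t = 2.160) it is 0.514; at n = 25 (t = 2.069) it is 0.396. So 0.48 falls short at n = 15 and passes at n = 25, and 0.54 passes at both.

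**4. The same illustration reversed**

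If uptake instead tracks the deficit present on the scan day at 0.60, and entry severity matters only through that deficit, the entry score becomes the attenuated one: again 0.30 to 0.48 for r₁₂ of 0.5 to 0.8. The documents do not say which case applies. The two scores answer different questions, and the plan currently names only one of them.

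**The case against.** Several counter-arguments carry weight.

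- **Time point.** Section 12.4 states none, and the days that close the endpoint bullet could attach to the PET measures or to the functional outcomes. This stands as a reading of the sentence. But no other NIHSS is scheduled, so following the plan leads to the Day 15 and Day 90 scores.
- **Other severity measures.** A reader might infer that the whole severity analysis becomes a second outcome analysis and can say nothing about the initial insult. The documents do not support that. Infarct volume and size are named in 6.1 and 12.4, and a separate endpoint relates infarct volume to thalamic uptake. Only the clinical part is affected.
- **Day 15.** A reader might infer that both later scores are residual deficit after recovery. That fits Day 90. Day 15 can fall 2 days after Screening and is at most a partly recovered score.
- **Weaknesses of the entry score.** It may be taken anywhere from day 0 to day 10, and criterion 4 cuts it off below 5, which restricts its range and tends to lower its correlations. Both points stand.
- **Concurrent NIHSS.** Relating same-day deficit to same-day uptake is a legitimate exploratory question, so those correlations should not be dropped.
- **Later SAP.** It could give the entry score a role, but only if the value is recorded as study data, and the Schedule does not list it.

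**Conclusion.** The point holds for the clinical, non-imaging part of the severity analysis. Criterion 4 and the Schedule do not match, and the score that describes severity at entry has no stated use. As written, the plan assesses clinical severity only at the visits that also supply mRS and BI, which mixes initial severity with recovery clearly at Day 90 and partly at Day 15.

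The comparison of 0.30–0.48 with 0.60 is an illustration only. It rests on an assumed correlation of 0.60, an assumed entry-to-later correlation of 0.5 to 0.8, and no link between uptake and recovery once entry severity is given. The significance threshold is also an assumption, and n may be anywhere from 15 to 25. A reader might infer that the planned analysis will miss a real association; the documents do not support that, because the result changes with n, with r₁₂ and with the direction of the assumption. For an exploratory cohort this is a worthwhile, low-cost correction and not a fatal flaw.

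**What to change.** 1. In the Schedule of Events, add NIHSS to the Screening column, and record the score with its day since stroke onset.
2. In 6.1 and 12.4, name Screening NIHSS as the clinical measure of initial stroke severity, alongside infarct volume and size, and correlate Day 15 and Day 90 uptake with it.
3. Keep the correlations with Day 15 and Day 90 NIHSS, labelled as concurrent deficit, with Day 90 also labelled as outcome.
4. In the SAP, note the two limits of the entry score when interpreting it: the variable Screening day and the cut-off at 5. With 15 to 25 patients, estimates with confidence intervals are more informative than significance tests.

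Cost: wording in 6.1, 12.4 and the SAP, one Schedule entry and one data field, through a protocol amendment. Eligibility already requires the score, so patients face no added assessment. It also adds one set of exploratory correlations to report.
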